5.2.4. Analyses for Categorical Data

Categorical endpoints will be summarized using number and percentage. Shift table from baseline to Day 8 and Day 15 will be provided for lesion ISGA.

5.3. Methods to Manage Missing Data

Missing will not be imputed for efficacy descriptive summary. For continuous endpoints analyzed using mixed model in the double blinded period, the missing values post-randomization will be handled in a linear mixed-effect model with repeated measures for this continuous variable, where the values are assumed to be missing at random.

Non responder imputation (NRI) will be used for missing values of lesion ISGA response of clear or almost clear and at least a 2 grade improvement from baseline at Day 8 and Day 15. No imputation for missing values of ISGA response of clear or almost clear and at least a 2 grade improvement from Day 15 to Day 43.

In addition, missing values for safety endpoints will not be imputed.

6. ANALYSES AND SUMMARIES

6.1. Primary Endpoint(s)

6.1.1. Change In Lesion TSS From Baseline To Day 15

6.1.1.1. Primary Analysis

- Analysis time points: Day 15.
- Analysis population: FAS.
- Analysis methodology: the intra-subject difference of change from baseline in lesion TSS between crisaborole and vehicle up to Day 15 will be analyzed using the model specified in [Section 5.2.2](#).

- Imputation for missing values: observed data will be included in the model, the missing values will be handled in the model, where the values are assumed to be missing at random.
- Supporting objective and Decision rule: Primary Objective, the lesion TSS change is superior for crisaborole treated area if $pvalue < 0.05$.

Reporting results:

- Raw data: The sample size, mean, standard deviation, median, Q1, Q3, minimum and maximum at baseline and post-baseline visits will be presented for each treatment.
- Change from baseline: The sample size, mean, standard deviation, median, Q1, Q3, minimum and maximum will be presented for each treatment. The LS means of difference and the corresponding standard error, 95% CI, p-value will be presented.

Figures

- Line plots of the means change from baseline at Day 15 and 8 for two treatments.

6.1.1.2. Sensitivity/Robustness Analyses

To support the interpretation of the primary analysis the following analyses will be performed:

6.1.1.2.1. Analysis for PPAS

- Analysis time points: up to Day 15.
- Analysis population: PPAS.
- Analysis methodology: the intra-subject difference of change from baseline in lesion TSS between crisaborole and vehicle will be analyzed using the model specified in [Section 5.2.2](#).
- Imputation for missing values: observed data will be included in the model, the missing values will be handled in the model, where the values are assumed to be missing at random.
- Supporting objective and Decision rule: Primary Objective, the lesion TSS change is superior for crisaborole treated area if $pvalue < 0.05$.

Reporting results:

- Raw data: The sample size, mean, standard deviation, median, Q1, Q3, minimum and maximum at baseline and post-baseline visits will be presented for each treatment.

- Change from baseline: The sample size, mean, standard deviation, median, Q1, Q3, minimum and maximum will be presented for each treatment. The LS means of difference and the corresponding standard error, 95% CI, p-value will be presented.

6.1.2. Change in Key Skin Biomarkers (S100A12, CCL17, CCL18, CCL22, K16, elafin/PI3 and IL-13 expression level) From Baseline to Day 15

6.1.2.1. Primary Analysis

- Analysis time points: Day 15.
- Analysis population: PPAS.
- Analysis methodology: the change from baseline in lesion biomarkers will be analyzed using the model specified in [Section 5.2.3](#).
- Imputation for missing values: observed data will be included in the model, the missing values will be handled in the model, where the values are assumed to be missing at random.
- Supporting objective and Decision rule: Primary Objective, the lesion biomarker change is superior for crisaborole treated area if adjusted pvalue<0.05.

Reporting results:

- Raw data: The sample size, mean, standard deviation, median, Q1, Q3, minimum and maximum at baseline and post-baseline visits will be presented for each treatment.
- Change from baseline: The sample size, mean, standard deviation, median, Q1, Q3, minimum and maximum will be presented for each treatment. The LS means of difference and the corresponding standard error, 95% CI, p-value will be presented.

6.2. Secondary Endpoint(s)

6.2.1. Change in The Lesion TSS From Baseline to Day 8

Day 8 is a time point in the mixed model for the primary analysis for lesion TSS change from baseline at Day 15. The analysis for lesion TSS change at Day 8 is from the same model, and data reporting is same as for Day 15. See [Section 6.1.1](#).

6.2.2. Changes in Key Skin Biomarkers From Baseline to Day 8

Day 8 is a time point in the mixed model for the primary analysis for biomarkers change from baseline at Day 15. The analysis for biomarkers change at Day 8 is from the same model, and data reporting is same as for Day 15. See [Section 6.1.2](#).

6.2.3. Correlation Between Biomarkers Change And Lesion TSS Change

The analysis for correlation between change from baseline to Day 15 in key biomarkers and change from baseline to day 15 in lesion TSS will be performed by treatment. Pearson correlation coefficient will be presented.

6.2.4. Change From Baseline to Day 8 and Day 15 in ISGA

6.2.4.1. Primary Analysis

- Analysis time points: Day 8 and Day 15.
- Analysis population: FAS.
- Analysis methodology: the intra-subject difference of change from baseline in lesion ISGA between crisaborole and vehicle will be analyzed using the model specified in [Section 5.2.2](#).
- Imputation for missing values: observed data will be included in the model, the missing values will be handled in the model, where the values are assumed to be missing at random.

Reporting results:

- Raw data: The sample size, number and percentage for each category at baseline and post-baseline visits will be presented for each treatment.
- Change from baseline: The sample size, mean, standard deviation, median, Q1, Q3, minimum and maximum will be presented for each treatment. The LS means of difference and the corresponding standard error, 95% CI, p-value will be presented.
- Shift table: number and percentage from each category at baseline to each category at Day 8 and Day 15 will be presented.

6.2.5. Change From Baseline To Visits Up To Day 15 In Pruritus Numerical Scale

- Analysis time points: Day 2 to Day 15
- Analysis population: FAS
- Analysis methodology: the intra-subject difference of change from baseline in lesion pruritus between crisaborole and vehicle will be analyzed using the model specified in [Section 5.2.2](#).
- Imputation for missing values: observed data will be included in the model, the missing values will be handled in the model, where the values are assumed to be missing at random.

[figure not shown]
Reporting results:

- Raw data: The sample size, mean, standard deviation, median, Q1, Q3, minimum and maximum at baseline and post-baseline visits will be presented for each treatment.

[figure not shown]
- Change from baseline: The sample size, mean, standard deviation, median, Q1, Q3, minimum and maximum will be presented for each treatment. The LS means of difference and the corresponding standard error, 95% CI, p-value will be presented.
- Plot: Line plot will be provided for mean change (\pm SE) from baseline.

CCI

CCI

6.4. Subset Analyses

N/A

6.5. Baseline and Other Summaries and Analyses

6.5.1. Baseline Summaries

Demographic and baseline characteristics will be summarized for safety analysis set according to Pfizer data standards. Lesion baseline data will be summarized by treatment.

6.5.2. Study Conduct and Subject Disposition

Subjects evaluation, disposition, discontinuation will be summarized for safety analysis set according to Pfizer data standards.

6.5.3. Study Treatment Exposure and Compliance

The exposure to study drug in each treatment group in double blind period will be summarized by total number of applications, the total number of days of dosing, and number and percentage of subjects who are compliant with the dosing regimen. The exposure to crisaborole in open label period will be summarized as well.

For double blind period, a subject is considered compliant with the dosing regimen if the subjects:

- *not miss more than 6 IP applications during the double-blind treatment period;*
- *and have no missed IP applications the 2 days before Day 15 biopsy collection;*
- *and not miss more than 3 IP applications in total before Day 8;*
- *and have no missed IP applications the 2 days before Day 8 biopsy collection (if collected).*

For open label period, a total of 56 doses are expected to be applied. A subject will be considered compliant with the dosing regimen if they receive at least 45 but no more than 67 investigational product doses (ie, 80 – 120%, inclusive, of the expected number of doses) administered in accordance with the protocol.

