Pruritus numerical rating scale (global)		X				X	X k	X	X	
Contraception Check g	X	X	X	X	X	X	X		X	X
Serious and non-serious adverse event monitoring	X	→	→	→	→	X	→	→	→	X

Abbreviations: → = ongoing/continuous event; AD = atopic dermatitis; BID = twice a day; % BSA = percent of body surface area; CRU = Clinical Research Unit; CCI [redacted]; ET = Early termination visit; FSH = follicle-stimulating hormone; ISGA = investigator's static global assessment; CCI [redacted]; TSS = Total Sign Score.

- Follow-up contact will be completed at least 28 calendar days after the last administration of the investigational product to capture any potential adverse events and to confirm appropriate contraception usage. Visit is planned to occur as a telephone contact.
- The Screening physical examination (full) may be performed at Baseline/Day 1 visit at the discretion of the Investigator. If full exam is completed at Screening, a limited exam should be collected at baseline. Target treatment areas must be identified at Screening and confirmed at Baseline.
- Women of childbearing potential only. Serum pregnancy test at Screening and urine pregnancy tests at all other visits.
- From Day 1 to Day 15 study treatment will be applied at the site (CRU), at regular intervals twice a day, approximately every 8 to 12 hours. From Day 15 through the end of treatment, subjects will apply open-label investigational product at home twice a day, approximately every 8-12 hours. During the open-label period, subjects will be required to complete the diary which will include dosing, adverse events and pruritus numerical rating scale information.
- On Day 15 study visit, a diary will be distributed to the subject. There will be a requirement to bring the subject diary to the subsequent visit(s) for collection and review.
- One 4.5 mm skin biopsy will be collected from each target treatment area prior to IP application on Day 1, Day 8 (optional for subjects) and Day 15. The biopsies on Day 8 and Day 15 will be collected in the vicinity, but at least 1 cm distant from where the biopsies were collected at Day 1, even if the target treatment area has cleared. One additional 4.5 mm skin biopsy will be collected from nonlesional skin on Day 1. If a subject has an early termination visit during the double-blind treatment period, every attempt should be made for the skin biopsy to be collected at this visit.

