#### **5.4.2. Preparation and Dispensing**

Investigational product should be prepared and dispensed by an appropriately qualified and experienced unblinded member of the study staff (eg, study coordinator, physician, nurse, physician's assistant, nurse practitioner, pharmacy assistant/technician, or pharmacist) as allowed by local, state, and institutional guidance.

For IP application during the double-blind treatment period, one tube of crisaborole and one tube of vehicle will be dispensed for each subject and assigned, as per [Section 5.2](#), to the target treatment areas. Upon assignment, the unblinded staff will indicate subject number on

the product label(s) in the designated area. Each dose will be prepared by qualified unblinded site personnel. Each dose will be prepared by weighing the investigational products to ensure accurate application rate of 3 mg/cm^2 to an area of 10 cm x10 cm. The investigational product will be administered in blinded fashion to the subject by blinded site staff.

Refer to the Investigational Product Manual (IP manual) for instructions on how to prepare the investigational product for administration.

Open-label crisaborole 2% ointment tubes and cartons will be dispensed at the Day 15 visit for self-application by the subject. A qualified staff member will dispense the investigational product in the cartons provided, in quantities appropriate for the study visit schedule and subjects' requirements. On Day 15, the site should dispense an adequate amount of investigational product used until the subject returns for the Day 43 visit (end of treatment/early termination).

The first dose of the open-label treatment period should be performed at the CRU after the Day 15 biopsy sample collection. The subject should be instructed how to apply the product, and maintain the subject diary. The subject should also be instructed to maintain the product in the tubes and cartons until dosing and return all dispensed supplies (unused/partial/empty) at the next study visit.

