### **6.5. Day 15 (+1 day)**

Subjects will return to CRU on Day 15 and the following procedures will be completed:

- Review concomitant treatments.
- Assess symptoms by spontaneous reporting of AEs.
- Confirm and document that proper contraception is being used for the subject and their partner, as appropriate.
- Collect Urine pregnancy test.
- ISGA.
- Lesion ISGA.
- CCI [REDACTED]
- Lesion TSS.
- CCI [REDACTED]

- Pruritus Numerical rating scale (global and for each target lesion).
- Skin biopsy collection.
- Dispense open-label investigational product for outpatient administration.
- Train subject on correct application of IP.
- Subject diary training & distribution.
- Subject application of the open-label IP to all AD lesions with oversight of the study site.
- Completion of initial subject diary entry of the open-label IP with oversight and training by the study site.

**After Day 15 dosing**, the following procedures will be completed:

- AE collection.
- The subject may be discharged from CRU immediately post-dose application.

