#### **6.7. Days 16 to 42 Outpatient/Home based Dosing**

Approximately every 8-12 hours until Day 43 (end of treatment/early termination) visit, the subjects will apply open-label IP at home to all AD lesions (excluding scalp), complete the subject diary and maintain all IP supplies. The subjects will be instructed how to complete the diary, which will include dosing, AEs and pruritus numerical rating scale information.

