#### **6.8. Day 43 ( $\pm 3$ days) - End of treatment/Open-label Early Termination**

Subjects will return to the CRU on Day 43 (end of treatment/early termination) for an outpatient visit and the following procedures will be completed:

- Collection and review of subject diary.
- Confirm and document that proper contraception is being used for the subject and their partner as appropriate.
- Perform a limited physical examination.

- Collect urine pregnancy test.
- Collect all IP tubes and cartons (full/partial/empty) returned by the subject.
- Collect safety laboratory tests.
- ISGA.
- CCI [REDACTED]
- Pruritus Numerical Rating Scale (global only).
- Review concomitant treatments.
- AE collection.

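### Open-label compliance is set at 80–120% of a fixed 56 doses, but within the protocol's visit windows completers are due about 48 to 62, so the 45-dose floor is really 94% to 73%

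*SAP*

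**What the plan says.** SAP 6.5.3 gives one denominator for all subjects: "For open label period, a total of 56 doses are expected to be applied". The criterion follows: "A subject will be considered compliant with the dosing regimen if they receive at least 45 but no more than 67 investigational product doses", glossed as "80 – 120%, inclusive, of the expected number of doses". The section does not adjust the expected number for actual visit dates and does not mention subjects who stop early.

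The protocol lets the length of open-label treatment vary:

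- **Start.** "The first dose of the open-label treatment period should be performed at the CRU after the Day 15 biopsy sample collection" (Protocol 5.4.2). Protocol 6.5 gives the Day 15 visit a window of +1 day.
- **Frequency and duration.** "From Day 15 through the end of treatment, subjects will apply open-label investigational product at home twice a day" (Schedule of Activities, footnotes). Protocol 6.7 is headed "Days 16 to 42 Outpatient/Home based Dosing", but its text has subjects applying product until the Day 43 visit.
- **End.** Protocol 6.8 gives the Day 43 visit a window of ±3 days. The same visit serves as "End of treatment/Open-label Early Termination".

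The protocol sets no numeric threshold for open-label compliance. Section 5.3 provides only for diary recording and review by site staff.

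**The concern.** A rule stated as a percentage of expected doses should mean the same thing for every subject who follows the protocol. Here it does not. A subject whose visits fall early or late, but within the windows, is due fewer or more than 56 doses and is still judged against 45 and 67.

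Two errors of classification become possible among completers. A subject with a long course can miss well over 20% of doses due and be called compliant. A subject with a short course can take well over 80% and be called non-compliant. The percentage compliant then mixes adherence with visit scheduling, and a reader of the study report could not separate the two from that figure.

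**Working it through.** **Reproducing the SAP's figures.** Days 15 to 42 are 28 days. 28 × 2 = 56 doses. 0.80 × 56 = 44.8, rounded up to 45. 1.20 × 56 = 67.2, rounded down to 67. All three figures are correct for the nominal schedule.

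**Inputs for the window check.** Two doses a day (Schedule of Activities); start on Day 15 or 16 (Protocol 6.5); end-of-treatment visit on Day 40 to 46 (Protocol 6.8); limits of 45 and 67 (SAP 6.5.3).

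**Assumption.** Two doses on each day from the first open-label day to the day before the end-of-treatment visit.

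**Formulas.** Doses due = 2 × (visit day − start day). Effective floor = 45 / doses due. Effective ceiling = 67 / doses due. Own 80–120% range = 0.80 × due rounded up, to 1.20 × due rounded down.

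| Start | Visit | Doses due | 45 / due | 67 / due | Own 80–120% |
|---|---|---|---|---|---|
| Day 16 | Day 40 | 48 | 93.8% | 139.6% | 39–57 |
| Day 15 | Day 40 | 50 | 90.0% | 134.0% | 40–60 |
| Day 16 | Day 43 | 54 | 83.3% | 124.1% | 44–64 |
| Day 15 | Day 43 | 56 | 80.4% | 119.6% | 45–67 |
| Day 16 | Day 46 | 60 | 75.0% | 111.7% | 48–72 |
| Day 15 | Day 46 | 62 | 72.6% | 108.1% | 50–74 |

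**Who changes class.** With 62 doses due, a subject who took 45 to 49 passes the SAP rule but is below 80% of doses due; 62 − 45 = 17 doses may be missed, against 62 − 50 = 12 under the stated percentage. With 48 due, a subject who took 39 to 44 fails the SAP rule but is at or above 80%; only 48 − 45 = 3 doses may be missed, against 48 − 39 = 9.

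**Sensitivity to the assumption.** One dose more or fewer (a late biopsy on the first day, or a dose on the final visit day) moves the 62-dose case to 71.4–73.8% and the 48-dose case to 91.8–95.7%. If the ±3 days were counted from the actual Day 15 visit, the course would be 25 to 31 days, 50 to 62 doses, and the floor 90% to 73%.

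**Small departures.** From a Day 15 start, a visit on Day 42 gives 45/54 = 83.3% and a visit on Day 44 gives 45/58 = 77.6%.

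**The case against.** The strongest reply is that a fixed denominator is a legitimate definition. The SAP measures compliance with the planned regimen, that regimen is nominally 28 days, and a subject who stops early did not receive it. For early stoppers this stands. From a Day 15 start, full dosing through Day 36 gives 22 × 2 = 44 doses, so a subject who stops by then fails even with every dose taken. A reader might infer that such subjects are wrongly labelled, but the documents do not support that: counting early stopping against the planned course is a defensible choice. The opposite choice has its own cost. Protocol 6.10 keeps subjects who discontinue product in the study, so ending the denominator at the last day of treatment would score someone who quit on Day 20 as fully compliant. SAP 6.5.2 already summarises discontinuation separately. The reply does not cover completers, who followed the protocol and still meet different thresholds.

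It is also fair that the extremes are corner cases. The documents give no distribution of visit days, so the number of subjects affected cannot be stated, and a visit one day off nominal moves the floor by only about three percentage points.

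Two stronger readings are tempting. The first is that the SAP contains an arithmetic error; it does not, as the nominal figures reproduce. The second is that the double-blind rule in the same section treats early stopping the opposite way, because it counts missed applications and someone who stops on Day 3 has missed none. That is not established. The limit of six applies to the whole double-blind period, which Protocol 3 and SAP 2.2 run to the Day 15 biopsy. On that reading a subject who stops after Day 3 has received 6 of 28 applications (Days 1 to 14, twice daily) and missed 22, and fails there too.

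**Conclusion.** The point holds for subjects who complete open-label treatment within the permitted windows. The fixed 56 makes the stated percentage limits untrue for any course other than 28 days: at the edges of the windows the floor runs from 94% to 73% and the ceiling from 140% to 108%. This rests on the two-doses-a-day assumption and on dosing continuing up to the actual visit, as the text of Protocol 6.7 indicates. If home dosing ended on Day 42 whatever the visit date, as the heading of that section could suggest, no course would exceed 56 doses and only the short-course half of the problem would remain.

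The importance is low. Open-label compliance is a descriptive summary. It defines none of the analysis sets in SAP 4, and both primary endpoints are measured at Day 15. There is no conflict with the protocol, which gives no open-label threshold.

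**What to change.** In SAP 6.5.3, define expected open-label doses for each completer as 2 × the number of days from the first open-label application to the day before the actual end-of-treatment visit, and apply 80–120% to that number. The nominal course keeps its limits of 45 and 67.

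Add one sentence for subjects who stop product early: either they are judged against the planned 56, or they are judged against 56 and an on-treatment percentage is shown as a separate additional line. Early stopping should not be able to count as full compliance.

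The cost is two sentences of SAP text and one derivation. The visit dates and diary dosing records are already collected. The denominator will differ between subjects, so the table needs a footnote giving the definition. Nothing about dosing or visit scheduling changes.

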6.5.4. Concomitant Medications and Non-Drug Treatments

Prior drug and non-drug treatment, concomitant drug and non-drug treatment will be summarized according to Pfizer data standards.

6.6. Safety Summaries and Analyses

6.6.1. Adverse Events

Adverse events will be summarized according to Pfizer data standards for each phase.

- TEAEs.
- Serious AEs.

AEs will not be double counted across phases. Counting of AEs will be based on start date of AE. If the start date of an AE is in the double blind period, the end date of the AE in the open label period and severity of AE remained the same in both phases or became lower, then the AE will be counted in double blind period, not in the open label period. However, if the same AE started in the double blind period, and get worse in severity in the open label period, then the AE will be counted in both phases.

Lesion TEAEs and SAEs in double blind phase will be summarized by treatment. General TEAEs and SAEs will be summarized for overall safety analysis set.

TEAEs will be summarized by the number of subjects reporting any TEAE, system organ class (SOC), preferred term, severity, relationship to investigational product, and seriousness.

Serious adverse events (SAEs) will be summarized by SOC and PT, and individual SAEs will be listed by subject. A list of subjects who prematurely discontinue from the study due to an AE will be provided. (If no SAE or few SAEs, SAE summary table may not be needed. Listing would be enough).

